5.2.2. Analyses of Non-Longitudinal Continuous Data

The non-longitudinal continuous data will generally be analyzed by ANCOVA with treatment as the factor and baseline disease severity as covariates. When modeling the change from baseline values, the variable for visit will start with the first post-baseline visit, and the actual baseline value will be included as a covariate. At each visit, estimates of least square mean (LSM) values and the LSM differences between treatment groups will be derived from the model. The corresponding p-values and 95% confidence intervals will also be derived from the model. The model will be used in the analysis of Change from Baseline at Week 12 in Peds FACIT-F.

For the Immunogenicity Sub-Study, natural logarithm of the IgG concentration data will be used for analysis. For the fold increase 4 weeks post-vaccination the ratio (post: pre) of concentration values will be calculated. Ratio values will be logarithmically transformed for analysis purposes. The geometric mean fold rise (GMFR) and geometric standard deviation of these fold rises will be calculated for each treatment arm. A 95% CI for this GMFR and the GMFR ratio will be constructed by back transformation of the CI for the logarithmically transformed GMFRs and the difference computed using the Student's *t* distribution.

5.2.3. Analyses of Longitudinal Continuous Data

Mixed-effect, repeated measures (MMRM) models will be used. The fixed effects of treatment, visit, treatment-by-visit interaction and baseline disease severity will be included. Visit will be modeled as a categorical covariate. Unstructured covariance matrix will be assumed for the model errors. Compound symmetry covariance matrix will be used if the model with unstructured variance covariance doesn't converge.

When modeling the change from baseline values, the variable for visit will start with the first post-baseline visit, and the actual baseline value will be included as a covariate. At each visit, estimates of least square mean (LSM) values and the LSM differences between treatment groups will be derived from the model. The corresponding p-values and 95% confidence intervals will also be derived from the model. In the model all patients with baseline data are used for estimating baseline covariate effects and adjusting LS means.

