3.2. Secondary Endpoint(s)

3.2.1. Key Secondary Efficacy Endpoints

The key secondary efficacy endpoints are:

- Response based on ≥ 4 points improvement from baseline in the Peak Pruritus Numerical Rating Scale (NRS) from baseline at Weeks 2, 4, and 12.
- Change from baseline in Pruritus and Symptoms Assessment for Atopic Dermatitis (PSAAD) total score at Week 12.

Detailed descriptions of how the Peak Pruritus NRS and PSAAD are derived are provided in Appendix 6 and Appendix 7, respectively.

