5. GENERAL METHODOLOGY AND CONVENTIONS

5.1. Hypotheses and Decision Rules

PF-04965842 200 mg QD will be declared superior to placebo if the null hypothesis of no difference between PF-04965842 200 mg QD versus placebo for **both** co-primary endpoints is rejected at the 5% significance level. Similarly, PF-04965842 100 mg QD will be declared superior to placebo if the null hypothesis of no difference between PF-04965842 100 mg QD versus placebo for **both** co-primary endpoints is rejected at the significance level specified below.

[figure not shown]
The familywise Type-I error rate for assessing the co-primary and key secondary endpoints will be strongly controlled at 5% (2-sided) using a sequential, Bonferroni-based iterative multiple testing procedure.

The procedure will first assess the co-primary endpoints (IGA and EASI-75 at Week 12 for 200 mg QD vs placebo) at the 5% level. If this hypothesis is not rejected, then all subsequent hypotheses will not be considered statistically significant. If this hypothesis is rejected, then assessing for statistical significance will continue as follows:

- The hypothesis for severity of pruritus (Peak Pruritus NRS4) 200 mg QD vs placebo at Week 2 will be assessed at the 2.5% level. If this hypothesis is rejected, then the unused alpha level of 2.5% will be passed on to the assessment for the key secondary endpoints and the co-primary endpoints for 100 mg QD vs placebo, in the order specified in Sequence A at a 5% significance level (see figure below). All subsequent hypotheses from any point where a hypothesis cannot be rejected will not be considered statistically significant.

- If the hypothesis for severity of pruritus (Peak Pruritus NRS4) 200 mg QD vs placebo at Week 2) is not rejected at the 2.5% level, then the hypotheses for the key secondary endpoints and the co-primary endpoints for 100 mg QD vs placebo, in the order specified in Sequence A will be assessed at a 2.5% significance level (see figure below). If all hypotheses in this sequence are rejected, then the unused alpha level of 2.5% will be passed on to the assessment of the hypothesis for severity of pruritus (200 mg QD vs placebo) at Week 2 at the 5% level. All subsequent hypotheses from any point where a hypothesis cannot be rejected will not be considered statistically significant.

Figure 2. Schematic for Multiple Testing Procedure

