The figure above (Figure 2) illustrates the procedure showing the sequence of the tests. Hypotheses for all other endpoints not described here are to be tested at the nominal 5% (2-sided) significant level, without adjusting for multiple comparisons.

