6.2. Secondary Endpoint(s)

6.2.1. Key Secondary Endpoint - Weeks 2, 4, and 12 Peak Pruritus NRS4 Response

- Estimand strategy: Composite, Estimand 1 (Section 2.1.1).
- Analysis set: FAS (Section 4).
- Analysis methodology: CMH and normal approximation in Section 5.2.1. Participants must have baseline PP-NRS ≥ 4 to be included in the analysis.
- Intercurrent events and missing data: The intercurrent event is captured through the variable definition; for participants who drop out for any reason, the response will be defined as “non-responsive” after that point.
- The number of participants, number and percent of response at each specified timepoints along with the 95% confidence interval by normal approximation will be presented for each treatment arm.
- The CMH test p-value, the estimate of the difference in proportions of response at each specified timepoints along with the corresponding 95% confidence interval by CMH normal approximation will be presented for each PF-04965842 dose group versus placebo.

6.2.2. Key Secondary Endpoint - Change from Baseline in PSAAD at Week 12

- Estimand strategy: Hypothetical, Estimand 2 (Section 2.1.2).
- Analysis set: FAS (Section 4). Participants must have observed baseline measure to be included in the analysis.
- Analysis methodology: MMRM in Section 5.2.3 including change from baseline data for each Week from Weeks 1 – 12.
- Intercurrent events and missing data: All data collected will be utilized; a simple average of the available values recorded within a week will be used for the analysis as a weekly measure; if there’s no available values recorded within a week, PSAAD for the week is missing and will not be used for analysis.
- Number of participants included in the analysis will be presented for each treatment arm.
- The least square mean (LSM) of change from baseline in PSAAD along with the corresponding 95% confidence interval will be presented for each treatment arm at each Week.

- The LSM difference along with the corresponding p-value and 95% confidence interval will be presented for each PF-04965842 dose group versus placebo arm at each Week.

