6.2.3.3. Continuous Endpoints

- Endpoints:
 - Weeks 2, 4, 8 and 12 Change from Baseline and Percent Change from Baseline in %BSA;
 - Weeks 2, 4, 8 and 12 Percent Change from Baseline in EASI;
 - Weeks 2, 4, 8 and 12 Change from Baseline and Percent Change from Baseline in Total SCORAD score, SCORAD subjective assessments of sleep loss (VAS);
 - Percent Change from Baseline in PP-NRS from Days 2-15, Weeks 4, 8 and 12.
- Estimand strategy: Hypothetical, Estimand 2 (Section 2.1.2).
- Analysis set: FAS (Section 4). Participants must have observed baseline measure to be included in the corresponding analysis.
- Analysis methodology: MMRM in Section 5.2.3.
- Intercurrent events and missing data: All data collected will be utilized.
- Number of participants included in the analysis will be presented for each treatment arm.
- The least square mean (LSM) of change from baseline or percentage change from baseline along with the corresponding 95% confidence interval will be presented for each treatment arm at each specified time points.

- The LSM difference along with the corresponding p-value and 95% confidence interval will be presented for each PF-04965842 dose group versus placebo arm at each specified time points.

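### If the unstructured MMRM fails to converge, the only fallback is compound symmetry with model-derived errors, which can misstate the Week 12 PSAAD standard error in either direction (optional precaution)

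*SAP*

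**What the plan says.** SAP 5.2.3 assumes an unstructured covariance for the MMRM errors. Its only contingency is "Compound symmetry covariance matrix will be used if the model with unstructured variance covariance" does not converge. On inference the same section says "The corresponding p-values and 95% confidence intervals will also be derived from the model". It names no intermediate structure, sandwich error or degrees-of-freedom method. SAP 5.3.2 adds only REML under missing at random, and Protocol 9.4.2.2 describes the MMRM without a covariance structure.

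Two analyses with many time points use this rule:

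- **PSAAD.** The key secondary endpoint is "Change from baseline in Pruritus and Symptoms Assessment for Atopic Dermatitis (PSAAD) total score at Week 12" (SAP 3.2.1). SAP 6.2.2 analyses it with this MMRM, "including change from baseline data for each Week from Weeks 1" to 12. It falls under the familywise procedure of SAP 5.1. Sequence A is tested at 5% if the Week 2 pruritus test for 200 mg succeeds; otherwise the hypotheses "in the order specified in Sequence A will be assessed at a 2.5% significance level".
- **Peak Pruritus NRS.** SAP 6.2.3.3 lists "Percent Change from Baseline in PP-NRS from Days 2-15, Weeks 4, 8 and 12", with "Analysis methodology: MMRM in Section 5.2.3". This endpoint is outside the familywise procedure: "Hypotheses for all other endpoints not described here are to be tested at the nominal 5% (2-sided) significant level".

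**The concern.** Compound symmetry, by its usual meaning, assumes one variance at every visit and one correlation between any two visits. Symptom scores under treatment need not behave that way. Spread in change from baseline may grow as responders separate from non-responders, or shrink as scores approach the floor. If the variance at Week 12 differs from the average over Weeks 1-12, the model-derived Week 12 standard error is wrong, and so are the p-value and interval.

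A rising variance would inflate the false-positive rate of a test that counts toward the 5% familywise claim. A falling variance would widen intervals and cost power. Switching to another standard error after seeing the model fail would be a post hoc choice for a controlled endpoint, so the matter is best settled in the plan.

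**Working it through.** **Plan's own figures.** The documents give no SD, correlation or power for PSAAD, so there is no figure on this point to reproduce. The stated power for the co-primary endpoints with 75 per arm does reproduce: exact enumeration of Fisher's test gives 80.7% for IGA (12% vs 32%) and 96.1% for EASI-75 (23% vs 53%).

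**Inputs.** From the SAP: 75 per arm, three arms, 12 weekly PSAAD visits, REML, tests at 5% or 2.5% two-sided. Assumed: the SD profiles, AR(1) correlation 0.9 and 10% dropout.

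**Covariance parameters.** PSAAD: 12 × 13/2 = 78 unstructured, against 2 for compound symmetry. Peak Pruritus NRS, if fitted as one model: 14 days + 3 weeks = 17 time points, 17 × 18/2 = 153.

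**Closed form, complete data.** Reported SE ÷ true SE at Week 12 = R = √(mean of the 12 visit variances) ÷ (SD at Week 12). Type I error = 2[1 − Φ(z·R)], with z = 1.96 (5%) or 2.241 (2.5%).

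Example, SD rising linearly from 1.5 to 2.0: mean SD is 1.75 and the spread of the 12 SDs adds 0.5² × 13/132 = 0.0246. Mean variance = 1.75² + 0.0246 = 3.087, root 1.757, so R = 1.757/2.0 = 0.879. Type I error = 2[1 − Φ(1.722)] = 8.5%.

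**Simulation.** Arm-by-visit means, REML compound symmetry, 10% dropout with hazard depending on the last score, 10,000 trials per cell, Monte Carlo SE 0.1 to 0.3 points. Compound symmetry used a normal reference and sandwich a t with 225 − 3 = 222 df. Entries are type I error at nominal 5% (2.5%).

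| SD over Weeks 1-12 | R | Closed form, compound symmetry | Simulated, compound symmetry | Simulated, sandwich |
|---|---|---|---|---|
| 1.8 to 2.0, linear | 0.951 | 6.2% (3.3%) | 7.1% (4.1%) | 5.6% (2.9%) |
| 1.5 to 2.0, linear | 0.879 | 8.5% (4.9%) | 9.6% (5.6%) | 5.2% (2.8%) |
| 1.2 to 2.0, linear | 0.810 | 11.2% (7.0%) | 12.9% (8.6%) | 5.8% (3.2%) |
| 1.5 to 2.0 by Week 4, then flat | 0.962 | 5.9% (3.1%) | 6.8% (3.6%) | 5.3% (2.6%) |
| 1.2 to 2.0 by Week 6, then flat | 0.911 | 7.4% (4.1%) | 8.6% (5.0%) | 5.5% (3.0%) |
| Constant | 1.000 | 5.0% (2.5%) | 5.4% (2.8%) | 5.1% (2.5%) |
| 2.0 to 1.6, linear | 1.128 | 2.7% (1.1%) | 3.3% (1.5%) | 5.4% (2.8%) |
| 2.0 to 1.2, linear | 1.350 | 0.8% (0.2%) | 1.2% (0.4%) | 5.1% (2.7%) |

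True over reported SE (1/R) runs from 1.23 to 0.74. The simulated compound-symmetry rates exceed the closed form because, with dropout, compound symmetry also misstates how well earlier visits predict Week 12. Across 24 cells (eight profiles; no, random or score-dependent dropout), sandwich errors gave 5.0% to 5.9% at 5% and 2.3% to 3.2% at 2.5%.

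A second simulation, with 2,500 trials per scenario and 10% random dropout, agreed: 9.2% for SD rising 1.5 to 2.0, against 9.3% for random dropout in the first. Sandwich errors gave 5.4% to 6.1% over its five scenarios.

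**How often the fallback would be used.** I fitted the unstructured model by REML Fisher scoring (limit 50 iterations, 3 × 75, baseline and severity included), 100 fits per setting.

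- PSAAD: correlation 0.9 to 0.97, dropout 10% to 30%, missing weeks 0% to 20%, one setting floored at zero. All 400 of 400 fits converged.
- Peak Pruritus NRS as one 17-point model: 200 of 200 converged with 10% to 20% missing days, and 88 of 100 with correlation 0.99, 20% dropout and 30% missing days.

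**The case against.** The strongest reply is that this hardly ever matters. With no failures in 400 PSAAD fits, the approximate 95% upper bound on the failure rate is 3/400 = 0.75%. Even with the worst profile, and failure independent of the test result, average type I error would rise by about 0.0075 × (12.9 − 5.0) = 0.06 points. SAP 6.2.2 also helps convergence, because a PSAAD week is missing only when no diary value was recorded that week. That stands, with the caveat that the fits rest on assumed correlations and one algorithm, so they indicate rarity without proving it.

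Other points that stand:

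- The largest figures need the SD to rise all the way to Week 12. Protocol 2.2.2 reports that adults on 200 mg in Phase 2b improved on IGA and EASI to Weeks 4 and 6 and then held. That evidence is indirect, but it favours the plateau rows (6.8% and 8.6%) over the steepest linear one.
- The type I simulations omit the baseline and severity covariates in SAP 5.2.3. The relevant SDs are residual SDs after that adjustment, and the net effect is unknown.
- The normal and t references differ by about 0.1 point at the 5% level, which explains part of the small gap in the constant-SD row.
- These are error rates for one test, not familywise rates. PSAAD is claimed only after the 200 mg co-primary endpoints and every earlier test in Sequence A are rejected. The sequence figure is not shown, so PSAAD's position cannot be read.
- The SAP does not say that the pruritus time points form one model. SAP Appendix 2 handles Days 2-15 and the visit weeks differently, so separate, smaller models are possible.

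These points limit the weight of the concern. They do not change the fact that the named fallback gives a wrong standard error whenever Week 12 variance departs from the visit average.

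**Conclusion.** The concern holds as an optional precaution. If the fallback is used, the Week 12 PSAAD standard error can be wrong either way: the true standard error is 1.23 to 0.74 times the reported one over the profiles tried, and close to it when the variance is constant. Sandwich errors bring the test near its nominal level in every profile. The size and direction for this trial cannot be known, because they depend on assumed SDs, correlations and dropout. The trigger is probably uncommon. The co-primary CMH analyses and the sample size are not affected, and no loss of error control has been demonstrated.

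**What to change.** Add after the fallback sentence in SAP 5.2.3: *If any covariance structure other than unstructured is used, empirical (sandwich) standard errors will be used.*

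Preferably, also try a heterogeneous-variance structure before homogeneous compound symmetry, for example heterogeneous Toeplitz and then heterogeneous compound symmetry. Sandwich errors correct the standard error but not the bias that a misspecified covariance can cause under missing-at-random dropout; a closer structure limits that bias. The sandwich sentence should cover these structures too. In large-sample calculations with decaying correlation (11 SD profiles, three correlation shapes, complete data), heterogeneous compound symmetry with model-derived errors gave 3.6% to 4.3% instead of 5%. Heterogeneous Toeplitz, and the convergence of the heterogeneous structures, were not simulated.

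The cost is one SAP sentence, or two with the extra step, and a few lines of code. Intervals may be slightly wider if the fallback is used. Nothing changes if the unstructured model converges.

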5.2.4. Analyses for Categorical Data

The frequency and percentage for each category will be presented.

5.2.5. Analyses for Time to Event Data

For a participant who experiences the event, the time to event will be the study day corresponding to the actual date of the event or the earliest visit date at which the participant has already experienced the event. For all participants who have not experienced the event, their time to event will be right censored at the last available measurement time (or visit) used to define whether the participant experienced the associated event.

Time-to-event endpoints will be summarized using the Kaplan-Meier method and estimated survival curves will be displayed graphically. Graphs will describe the number of patients at risk over time. The median, quartiles and probabilities of an event at particular points in time will be estimated by the Kaplan-Meier method. Ninety five percent CIs for median and quartiles will be provided.

The log-rank test (stratified using baseline disease severity) p-value will be used for comparing time to event data between treatment groups.

5.2.6. Analyses of Tier-1 and Tier-2 Events

Number and percentage of participants with AEs over the duration of treatment will be provided for each treatment group. Tier-1 events will be analyzed using methods proposed by Chan and Zhang (1999).⁵ Tier-2 events will be analyzed using asymptotic methods proposed by Miettinen and Nurminen (1985).³ Risk differences (each PF-04965842 dose compared to placebo) and 2-sided 95% confidence intervals will be reported. P-values will also be reported for Tier-1 events. Tier-3 events will not be summarized separately but included within the summary of all AEs.

5.3. Methods to Manage Missing Data

In general, for analyses using descriptive statistics, missing values will not be imputed. In addition, for safety endpoints, missing values will not be imputed. Other methods for handling missing values are discussed below.

5.3.1. Binary Endpoints

For binary endpoints analyzed at each scheduled visit separately, visit windows (see Appendix 2) will be used to map all observed data into nominal visits. After mapping, for subjects who drop out for any reason, any data will be defined as “non responsive” at all subsequent visits after the last observed value; for other subjects, any observations missing intermittently (including baseline values) will be considered missing completely at random (MCAR) and will remain missing in the analysis.

Additional analyses that are will utilize the longitudinal nature of the binary endpoint. A Generalized Linear Mixed Model (GLMM) will be fit to the observed data (ie, without defining missing data due to dropout as “non-response”). The binary outcome will be modeled using a logistic normal distribution. Fixed factors will include treatment (PF-04965842 200 mg QD and 100 mg QD and the placebo group), visit (Weeks 2, 4, 8 and 12) and treatment by visit interaction. Visit will be modeled as a categorical covariate. A subject specific random intercept will be used to model the correlation within a subject over time (see Appendix 3). Missing observations for the active groups (PF-04965842 200 mg QD and 100 mg QD) will be imputed multiply using a tipping point analysis to estimate the treatment effect under the assumption that the missing data mechanism is missing at random (MAR) or more generally, is missing not at random (MNAR). Using the estimated posterior predictive distribution of the GLMM model parameters obtained using Markov Chain Monte Carlo (MCMC) methods, estimates of the posterior predictive probability of response will be calculated for each treatment group. For subjects with missing data at a visit, the posterior predictive response probability in each active group will

be re-defined as a weighted linear combination of the posterior predictive response probability from this group and the posterior predictive response probability from the placebo group, where the missing observations in placebo group are assumed to be missing at random (MAR) (see Appendix 3). These weights are fixed MNAR quantities for the active groups. A single imputation of the missing value will be sampled from a Bernoulli distribution with this corresponding shifted/re-defined probability of response for the active groups. This imputation will be repeated multiple times with different MCMC samples to obtain multiple completed datasets. For each such completed dataset, the estimates of the proportions and CMH-weighted difference of proportions between each active group and placebo will be obtained along with the associated standard errors using the methods in Section 5.2.1. Rubin's rule (Rubin, 1987)⁴ will be used to combine the multiple estimates and standard errors across the imputed datasets and provide p-values.

The above analysis can be repeated for different combinations of MNAR quantities which will be applied to the probability of response to assess when the conclusion might change (ie, tipping). Two important scenarios are included in the tipping point analysis framework. When the MNAR quantities are zero and the posterior predictive probabilities in the active dose groups are not shifted, results are obtained under an assumption of MAR for the missing data mechanism. Alternatively, at the other extreme, when the MNAR quantities are 1.0 for each active dose group, results are obtained under an assumption that the distribution of the missing responses after discontinuation of each active group is the same as that of the missing responses on the placebo arm. More detailed descriptions are provided in Appendix 3.

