7. DISCONTINUATION OF STUDY INTERVENTION AND PARTICIPANT DISCONTINUATION/WITHDRAWAL

7.1. Discontinuation of Study Intervention

In certain instances, it may be necessary for a patient to permanently discontinue study intervention (ie, study treatment). If study intervention is permanently discontinued, the participant will remain in the study to be evaluated for EOT assessments (per Schedule of activities).

Note that discontinuation of study treatment does not represent withdrawal from the study. Refer to Appendix 5 for discontinuation criteria.

See the Schedule of Activities for data to be collected at the time of intervention discontinuation and follow-up and for any further evaluations that need to be completed.

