8.5. Pharmacokinetics

During the study, blood samples (3 mL) to provide minimum 1 mL of plasma for PK analysis will be collected into appropriately labeled tubes containing dipotassium ethylenediaminetetraacetic acid (K₂EDTA) at times specified in the protocol.

Blood for PK analysis will be collected at the study site at the following time points:

- At 22 hours (± 30 min) after the participant's last dose taken on the day prior to the Week 8 visit (this corresponds to 2.0 hours (± 30 min) pre-dose relative to the dose taken at the Week 8 visit, assuming a regular dosing schedule of once every 24 hours).
- At 2.0 hours (± 30 min) post-dose at Week 12.

All efforts will be made to obtain the PK samples at the exact nominal time relative to dosing. The exact time of the sample collection is to be noted on the source document and data collection tool (eg, CRF). Samples obtained outside the windows specified in the Schedule of Activities will be considered a protocol deviation. For Early Termination (ET) visits, if the participant discontinues before Week 8 do not collect PK samples. If the ET visit occurs after Week 8, collect PK samples only if the participant takes the study intervention at the site visit.

- The plasma will be stored in appropriately labeled screw-capped polypropylene tube at approximately -20°C within 1 hour of collection.
- Further details regarding the collection, processing, storage and shipping of the blood samples will be provided in the lab manual.
- Samples will be analyzed using a validated analytical method in compliance with Pfizer standard operating procedures.
- The PK samples must be processed and shipped as indicated to maintain sample integrity. Any deviations from the PK processing steps, including any actions taken, must be documented and reported to the sponsor. On a case-by-case basis, the sponsor may make a determination as to whether sample integrity has been compromised. Any sample deemed outside of established stability, or of questionable integrity, will be considered a protocol deviation.
- As part of understanding the PKs of the study intervention, ^{CCI} [REDACTED]

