9. STATISTICAL CONSIDERATIONS

9.1. Estimands and Statistical Hypotheses

9.1.1. Estimands

The primary estimand of the main study is a composite estimand (accounting for both treatment adherence and response), defined according to the primary objective and is in alignment with the primary endpoint. It includes the following four attributes:

- Population: Participants with moderate-to-severe AD as defined by the inclusion criteria and exclusion criteria and are randomized;
- Variable: Response based on IGA and EASI-75 at Week 12 (co-primary endpoints) and any other binary outcome measures such as response based on NRS4, % BSA < 5%, EASI-50, EASI 90, EASI-100, SCORAD50, SCORAD75. Participants who discontinue from the study treatment for any reason are considered as treatment failures or non-responders;
- Intercurrent event: The intercurrent event is captured through the variable definition;
- Population-level summary: Proportion of participants who are responders in each treatment group and differences in proportions of responders between each PF-04965842 dose and placebo at Week 12.

The secondary estimand of this study is the hypothetical estimand, which estimates the effect as if all patients maintain their randomized treatment. It includes the following four attributes:

- Population: Participants with moderate-to-severe atopic dermatitis as defined by the inclusion criteria for the double-blind phase and are randomized;
- Variable: Change from baseline to Week 12 in a continuous outcome measure such as total scores obtained from EASI, NRS, SCORAD, %BSA, PSAAD, PtGA, HADS, POEM, CDLQI, EQ-5D-Y, DFI, Peds FACIT-F;
- Intercurrent event: All data after an intercurrent event (eg discontinuation of treatment), if collected, will be censored;
- Population-level summary: Difference in least-square means between each PF-04965842 dose and placebo.

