9.4.2.1. Analysis of the Primary Endpoints

The co-primary endpoints will be analyzed using the (Cochran–Mantel-Haenszel) test adjusted by baseline disease severity group (moderate and severe) and for a given dose both must achieve statistical significance to meet the primary objective. The difference between each active group and the placebo group in the proportion of participants achieving IGA response (similarly for EASI-75) along with its 95% confidence interval (using the normal approximation for the difference in binomial proportions) will be reported. If a participant withdraws from the study, then this participant will be counted as non-responder for endpoints after withdrawal. Additional secondary analyses will utilize missing at random (MAR) and missing not at random (MNAR) approaches (eg, longitudinal mixed models and tipping point analyses).

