Appendix 2. Definition and Use of Visit Windows in Reporting

Visit windows will be used for efficacy variables, and for any safety data that display or summarize by study visit. For other endpoints (eg, ECG, vital signs), visit windows will be applied for summary statistics by study visits if required.

Visit Label	Target Day	Definition [Day window]
Baseline	Day 1 (Day of first dose)	Last observation prior to and including day of first dose
Week 2	15	Days 2 to 22
Week 4	29	Days 23 to 43
Week 8	57	Days 44 to 71
Week 12	85	Days 72 to 99
Follow Up/End of Study		
Week 16	113	Days 100 to -

For the lab values, if the calculated study day for the labelled baseline visit is not study Day 1 but falls within 28 days before the start of the study dosing, then that data should be used for the baseline instead of leaving baseline missing.

For the other values, if the calculated study day for the labelled baseline visit is not study Day 1, but falls before the start of the study dosing, then that data should be used for the baseline instead of leaving baseline missing.

If two or more visits fall into the same window, keep the one closest to the Target Day. If two visits are equaled distant from the Target Day in absolute value, the later visit should be used.

Observations on the actual day will be used to analyze Days 2-15 Pruritus NRS. Weeks 2, 4, 8 and 12 Pruritus NRS will be based on the windowing method.

Safety analysis will follow CaPS.

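### The SAP's Week 12 non-response rule does not implement the protocol's composite estimand: an early-termination IGA/EASI on Days 72-99 stands as the Week 12 result, although protocol 9.1.1 makes that participant a non-responder

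*SAP*

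**What the plan says.** The event that turns a participant into a non-responder on the co-primary endpoints is described in three ways.

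- **Protocol 9.1.1 (Estimands):** "Participants who discontinue from the study treatment for any reason are considered as treatment failures or non-responders". The trigger is stopping treatment.
- **Protocol 9.4.2.1 (Analysis of the Primary Endpoints):** "If a participant withdraws from the study, then this participant will be counted as non-responder for endpoints after withdrawal". The trigger is leaving the study, and it acts only on later endpoints.
- **SAP 2.1.1, 5.3.1, 6.1.1.1 and 6.1.2.1:** the trigger is *drop out* for any reason. Neither document defines the term.

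Protocol 7.1 separates the first two events: "Note that discontinuation of study treatment does not represent withdrawal from the study". After stopping treatment, "the participant will remain in the study to be evaluated for EOT assessments", so efficacy data can exist after the last dose.

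SAP 5.3.1 gives the order of derivation. First, "visit windows (see Appendix 2) will be used to map all observed data into nominal visits". Then dropouts are set to non-response "at all subsequent visits after the last observed value". SAP Appendix 2 sets the Week 12 window at Days 72 to 99 (target Day 85) with no on-treatment condition, and adds: "If two or more visits fall into the same window, keep the one closest to the Target Day".

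**The concern.** The substantive conflict is between protocol 9.1.1 and SAP 5.3.1. The estimand needs an override: once treatment is stopped, the Week 12 outcome is failure, whatever is observed. The SAP rule is only a fill: it supplies non-response where no value follows and leaves every observed value alone. SAP 5.3.1 itself describes the rule as handling data missing because of dropout.

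The co-primary test for 200 mg opens the whole testing sequence (SAP 5.1), so the variable behind it should have one definition before unblinding. For an affected participant, Estimand 1 would also use the same observed value as the treatment-policy Estimand 3 (SAP 2.1.3.1), which is meant to use all collected data. The per-protocol analysis does not recover the intended estimand, because SAP Section 4 removes early stoppers instead of counting them as failures.

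**Working it through.** **Step 1. The route exists in the documents.** The Schedule of Activities (protocol 1.3) puts early termination in the Week 12 column, the visit at which the co-primary IGA and EASI are taken. Protocol 8.5 foresees such visits late in treatment: "If the ET visit occurs after Week 8, collect PK samples only if the participant takes the study intervention at the site visit". Take a participant whose last dose and termination visit fall on Day 75:

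- SAP 5.3.1 maps the visit to Week 12 (Days 72-99). No later treatment-period visit remains to be reset, so an IGA of 0 or 1 with a 2-point drop counts as a response.
- Protocol 9.1.1 makes the same participant a non-responder.
- The 4-week follow-up does not displace the value. For a last dose on Day 72 or later it is due on Day 72 + 28 = 100 or later, outside the window.

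**Step 2. The plan's own power figures.** With 75 per arm and two-sided 5% (protocol 9.2), IGA 12% v 32% gives 80.7% power and EASI-75 23% v 53% gives 96.1% with Fisher's test. The pooled normal approximation gives 84.8% and 97.2%. The stated figures of at least 80% and 96% reproduce.

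**Step 3. Participants exposed.** The documents give no discontinuation rate. Assumption: a share s = 5-15% stops early in each arm, spread evenly over Days 1-84. Day 84 is the last early-stopping day because protocol Section 8 (dosing at the clinic on visit days) and 8.5 (post-dose PK sample at Week 12) plan a dose at the Day 85 visit.

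- Last dose on Days 72-84: 13 of 84 days, 13/84 = 0.155.
- Exposed per arm = 75 × s × 13/84 = 0.58, 1.16 and 1.74 for s = 5%, 10% and 15%.
- Days 82-84 overlap the ±3-day visit window. Leaving them out gives 10/81 and 0.46-1.39 per arm.

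**Step 4. Shift in the treatment difference.** If exposed stoppers respond at the design rates, the SAP rule raises the IGA difference by s × 13/84 × 20 = 0.15-0.46 points and the EASI-75 difference by s × 13/84 × 30 = 0.23-0.70 points. If stoppers in both arms respond at the placebo rate, the expected shift is zero.

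**Step 5. Effect on the IGA verdict.** Simulated trials had 75 per arm and used an unstratified pooled z test, because the severity split is not given. Each trial was scored under both rules. The result depends on whether the design rates in protocol 9.2 already include non-responder scoring. If they do, completers respond at the design rate divided by (1 - s).

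| Design rates in protocol 9.2 | Stoppers respond at design rates | Stoppers respond at placebo rate |
|---|---|---|
| Exclude non-responder scoring | verdict differs in 1.1-3.6% of trials | 0.7-2.4% |
| Include non-responder scoring | 1.0-2.6% | 0.7-1.7% |

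The net change in power from the estimand rule to the SAP rule lies within about -0.6 to +1.3 points across these cases.

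**Step 6. Distance from the threshold.** At the design counts (24 v 9 of 75) the pooled proportion is 33/150 = 0.22, the standard error is √(0.22 × 0.78 × 2/75) = 0.0676, z = 0.20/0.0676 = 2.96 and p = 0.003. With placebo held at 9, 19 active responders give p = 0.036 and 18 give p = 0.056, so six active responders would have to be reclassified. At s = 15%, the expected number of exposed active responders is 1.74 × 0.32 = 0.56.

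**The case against.** The best defence is that most of the text agrees. Protocol 9.4.2.1 and SAP 2.1.1, 5.3.1 and 6.1 all apply non-response forward in time, and 9.1.1 is the exception because it gives no timing. SAP 5.3.1 also speaks of missing responses after discontinuation as if this were the same as dropout, and SAP 2.1.1 says that Estimand 1 accounts for treatment adherence. In practice, stopping treatment and leaving the study will often coincide. This shows what was probably intended, but it does not remove the conflict: protocol 7.1 separates the two events, and the rule to be programmed keeps the observed value.

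A reader might infer more than the documents support:

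- *Two programmers would get different counts because* drop out *is undefined.* On the termination route they would not. SAP 5.3.1 keeps the observed value under either meaning. The figures above compare 9.1.1 with 5.3.1, not two readings of one term.
- *Values from the 4-week follow-up also enter the Week 12 window.* A last dose on Days 44-71 would put that visit on Days 72-99, but the IGA and EASI rows of the schedule cannot be read by column in the text available. That they are done at follow-up is not established, so no figure is given for this route.
- *Estimand 1 collapses into Estimand 3.* It does so only for the one or two exposed participants per arm. For missing data, non-response and multiple imputation still differ.
- *The rule favours active treatment.* The direction depends on which stoppers respond, and the net effect takes either sign.

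SAP 5.3.1 leaves intermittently missing values out as MCAR, while SAP Appendix 1 labels the analysis as non-responder imputation (compare protocol 9.4.2.2). That is a separate item.

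**Conclusion.** The concern holds as a conflict between the protocol's composite estimand and the SAP's derivation rule on the co-primary endpoints, and neither document reconciles the two. It should be fixed before unblinding. The textual finding is firm. The size is modest and rests on an assumed 5-15% early stopping in each arm, even timing over Days 1-84, an unstratified test, and assumed response rates among stoppers. On that basis it concerns one or two participants per arm, and the verdict would change in a few per cent of trials at most. It does not threaten the design.

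**What to change.** 1. In SAP 2.1.1, 5.3.1, 6.1 and 6.2.1, replace *drop out* for Estimand 1 with permanent discontinuation of study treatment before completing the planned treatment period, identified from treatment disposition and last-dose date. Score these participants as non-responders at Week 12 and at every nominal visit after discontinuation, and apply this before windowing. Completers assessed at the Week 12 visit are unaffected.
2. Among the co-primary analyses, use post-discontinuation assessments for Estimand 3 only.
3. Reconcile protocol 9.4.2.1 with 9.1.1 so that both name the same intercurrent event.

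The cost is SAP wording and one derivation flag. Protocol 9.4 sends major changes to the co-primary analyses to an amendment, so a protocol clarification may be needed. Observed response rates may fall slightly.
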